10. POTENTIAL BENEFITS TO INTERVENTION SUBJECTS

Non-invasive brain stimulation has the potential to modify cognitive and affective status for older adults at risk for dementia but this has not yet been proven. The relatively modest risks associated with the activity are reasonable in light of its potential benefits. Participants will have the opportunity to receive a 4-week guided and supervised tDCS sessions (including visual attention task for each tDCS session) and interact with the study staff.

11. COSTS FOR PARTICIPATION

No

12. PAYMENT FOR PARTICIPATION

Participants will be compensated for up to \$170 for the entire study, including \$50 for each assessment, and \$20 for the blood draw. Study partner subjects will be compensated for up to \$60 for the entire study, including \$10 for each NPI completed at each of the 4 weeks of the intervention and post-intervention and follow-up assessments. We believe this is a reasonable amount for the time and effort a participant and their study partner subject will contribute to the study. In addition, participants will be provided reimbursements if they incur parking or transportation costs when attending study-related activities.

13. SUBJECT WITHDRAWALS

Participants may be excluded from the study without their consent or withdraw from the study at their own discretion.

Withdrawal Circumstances: Anticipated circumstances under which participants may be excluded from the research without their consent include:

- Medical conditions which make ongoing participation in the study unsafe for a participant (e.g., change in MRI eligibility, seizures, severe depression, and/or suicidal ideations)

- If the intervention subject withdraws then the study partner subject is automatically withdrawn

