fMRI data will be collected using a gradient echo-planar imaging sequence. Participants will undergo a 5-minute resting-state scan at first, being instructed to relax with their eyes open, followed by a 5-minute event-design ‘target among distractors’ visual search task. For the task, participants fixate on a black screen for a constant inter-stimulus interval of 1000ms, follow by 5500ms presentation of the search pattern. Participants’ task is to search for target symbol “申” (which was present for 50% of trials), shown among 6 distractors (e.g., “由”, “甲”, etc.). Participants are instructed to press one of two response buttons to indicate whether the target was present or absent.

Secondary endpoints:

- Study partner-rated NPS (frequency and severity scores from NPI and NPI-Q⁴⁶).

Other measures:

- Cognitive functions will be measured using tests from three different versions of the computer-based battery Executive Abilities: Measures and Instruments for Neurobehavioral Evaluation and Research (EXAMINER);
- Paper-based measures of cognitive functioning will be measured using two versions of the Rey Auditory Verbal Learning Test (RAVLT, Lists A&B and C&D) and the Brief Visuospatial Memory

Test-Revised (BVMT-R, Forms 1-3);

- Functioning in daily life will be measured with the self-report version of the Activities of Daily Living-Prevention Instrument (ADL-PI-self).
- Fatigue across 5 domains (general, physical, mental, and reduced motivation & reduced activity) will be measured using the Multidimensional Fatigue Inventory (MFI);
- Sleep habits and quality of sleep will be measured using the total score from the Pittsburgh Sleep Quality Index (PSQI);
- Depression will be measured using both the 15- and 30-item versions of the Geriatric Depression Scale (GDS);
- Risk of suicide (current & past) and current suicidal ideation will be measured using Columbia Suicide Severity Rating Scale (C-SSRS);
- Anxiety will be measured using both the state and trait anxiety scales from the State-Trait Anxiety Inventory (STA);
- Perception of stress will be measured using Perceived Stress Scale (PSS);
- Apathy will be measured using the 18-item self-report and informant-rated Apathy Evaluation Scales (AES);
- Quality of life (QoL) across multiple life domains (including physical health, mood, relationships, activities, ability to perform tasks) will be measured using the 13-item self-report and informant-rated Quality of Life in Alzheimer's Disease scales (QOLAD);

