Assessments: Fully eligible participants and their study partner subjects will be notified of their eligibility for the study. Baseline assessments need to be scheduled within one month of in-person cognitive screening. Participants will then be asked to complete baseline measures (assessment, MRI scan, and blood draw), after which they will be randomized to either the active or sham tDCS intervention condition. The blood draw may occur within 2 weeks (before or after) the baseline assessment and MRI scan. The beginning of the intervention phase will start within two weeks after the baseline assessment and blood draw. Follow-up cognitive assessments and MRI scans for each participant will occur within 2 weeks after completion of intervention (i.e., post-intervention assessment) and then 4 weeks after post-intervention assessment (i.e., follow-up assessment). We will allow 2 weeks to make up the follow-up assessment. At the same time points, study partner subjects will be administered the NPI, AES, and QOLAD. Follow-up assessments for study partners can also be conducted over the phone, at the partners discretion.

A detailed overview of data collection measures for screening and assessments can be found below in **Table 1**. To reduce the burden on participants, study partner subjects, and staff, as well as to avoid practice effects of cognitive measures, for individuals who are eligible for the study, their screening data will be used as baseline data; for those who are not eligible for the study, their screening data will only be used for summarizing the reasons for ineligibility.

Group assignment/randomization will be determined with a block-based matlab randomization.

Table 1: Study Measures I = intervention subject; P = partner subject

	Screening		Baseline	Interventions				Makeup Interventions (if needed)		Post-Intervention Assessments	
	Phone	In-Person		Week 1	Week 2	Week 3	Week 4	Week 5	Week 6	Immediate Post-Intervention	Final Post-Intervention
Study Activities											
Verbal Consent for Screening	I, P										
Inclusion/Exclusion (verified at In-Person)	I, P	I, P									
MRI Screening Form	I										
Informed Consent		I, P									
UBACC		I									
Demographics & background		I, P									
MoCA (V2)		I									
RAVLT		I (Lists C&D)								I (Lists A&B)	I (Lists C&D)
ADL-PI-self		I								I	I
PSS		I								I	I
PSQI		I								I	I
MFI		I								I	I
GDS-15		I		I	I	I	I	I	I		
AES		I, P								I, P	I, P
QoL-AD		I, P								I, P	I, P

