MRI scanning produces a loud tone that can cause damage to the inner ear if appropriate protection is not used. Adequate protections in the form of earplugs or close-fitting silicon-padded headphones will be provided.

We cannot guarantee direct benefits from participating in the MRI assessment. fMRI are unique techniques in their ability to non-invasively study human brain function.

Discovery of Previously Unknown Conditions (conditions that can be diagnosed from having access to research-quality MRI):

Our scans are not read by a neuroradiologist, and the intervention subjects are explicitly told that the experiment will not provide information regarding their health status. However, if the certified MRI technician suspects something abnormal, he/she will seek advice from a qualified neuroradiologist, and the subject will be notified that his/her MRI indicated a potentially abnormal finding. With the subject's permission we will send information to their physician.

If a participant withdraws from the study, all attempts will be made to collect data to allow for inclusion in the analysis. Reasons for withdrawal will be recorded.

Risk and Protection against Risk related to tDCS Conditions:

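### Withdrawing the study partner automatically conflicts with the promise to keep collecting data after withdrawal, and can cost the partner-rated NPI endpoint

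*Combined protocol and SAP*

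**What the plan says.** Section 13 allows two kinds of exit: "Participants may be excluded from the study without their consent or withdraw from the study at their own discretion". A list follows, introduced by "Withdrawal Circumstances: Anticipated circumstances under which participants may be excluded from the research without their consent include". It gives medical conditions that make continuing unsafe, with the examples "change in MRI eligibility, seizures, severe depression, and/or suicidal ideations". The next item under the same heading is the partner rule: "If the intervention subject withdraws then the study partner subject is automatically withdrawn".

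Section 9, at the end of the text on MRI risks, says: "If a participant withdraws from the study, all attempts will be made to collect data to allow for inclusion in the analysis".

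Section 4 defines the secondary endpoint as "Study partner-rated NPS (frequency and severity scores from NPI and NPI-Q"). Section 8 sets the source after treatment: "At the same time points, study partner subjects will be administered the NPI, AES, and QOLAD", the time points being the post-intervention and follow-up assessments. It adds: "Follow-up assessments for study partners can also be conducted over the phone, at the partners discretion". In Table 1 the full NPI comes from the partner at in-person screening and at the two post-intervention assessments. The NPI-Q comes from the partner at phone screening and in Weeks 1 to 4.

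Section 9 has a separate rule for neuropsychiatric symptoms that worsen during treatment. The event is reported, the intervention is discontinued and a psychiatric assessment follows. Leaving the study is not mentioned.

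**The concern.** Staff cannot follow both sentences for this endpoint. If the partner is withdrawn with the participant, no one remains who can give an NPI rating, and the promise in section 9 cannot be kept.

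The procedures visible in the protocol do not require this loss. The partner signs a separate consent (section 7), may be assessed by phone (section 8), and is already paid for ratings at both post-intervention visits (section 12). A participant who can no longer be scanned can still be rated by a partner over the phone.

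The loss may also be related to the outcome. Severe depression overlaps with an NPI domain, and section 9 uses the NPI Depression/Dysphoria item to detect suicidality risk. If exclusion for these reasons also removes the partner, the missing ratings would tend to be poor ones, and an arm that loses more of them would look better than it is. H2a and H2b both use change in NPI. Section 17 states no missing-data assumption, analysis population or sensitivity analysis. The study is meant to supply effect sizes for a later trial, so a bias here would carry forward.

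**Working it through.** **1. The plan's own figure.** Section 17 takes n = 36 and allows 10% attrition: 36 / 0.90 = 40, the planned total. So 0.10 × 40 = 4 exits are expected from all causes, or 2 per arm of 20 if balanced.

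**2. What is left after an exit, if the partner leaves too (Table 1).**

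| Time of exit | Full NPI after baseline | NPI-Q after baseline |
|---|---|---|
| During Weeks 1–4 | none | weekly ratings up to exit |
| After Week 4, before the first post-intervention visit | none | Weeks 1–4 |
| Between the two post-intervention visits | first visit only | Weeks 1–4 |

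The NPI-Q is not scheduled after Week 4, so it cannot replace the later full NPI.

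**3. Loss of precision.** Section 17 also uses r² = 0.20, two-sided alpha 0.05 (two-sided is my assumption; it reproduces the plan's n = 37) and power 0.80. With Fisher's z, power = Φ(atanh(√0.20) × √(n − 3) − 1.96). This gives 0.833 at n = 40 and 0.789 at n = 36. Losing four outcomes costs about 4 percentage points of power, which is minor.

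**4. Possible bias.** The documents give no NPI standard deviation and no exit rate by arm or cause, so this is a range under assumptions. Let lost participants be D standard deviations worse on NPI change than those who stay, with 20 per arm. Dropping *a* participants shifts an arm's mean by (a / 20) × D in the favourable direction. With *a* lost in one arm and *s* in the other, the bias in the arm difference is ((a − s) / 20) × D.

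| Split of 4 exits | (a − s) / 20 | D = 0.5 | D = 1.0 | D = 1.5 | D = 2.0 |
|---|---|---|---|---|---|
| 2:2 | 0 | 0 | 0 | 0 | 0 |
| 3:1 | 0.10 | 0.05 | 0.10 | 0.15 | 0.20 |
| 4:0 | 0.20 | 0.10 | 0.20 | 0.30 | 0.40 |

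**5. A worst-tail case.** Suppose one arm loses exactly its 2 worst of 20 and the other arm has no selective loss. For 20 normal values the expected two largest are 1.867 and 1.408 SD. The mean of the other 18 moves by (1.867 + 1.408) / 18 = 0.18 SD.

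Steps 4 and 5 compare observed means only. They give no credit for ratings made before exit, which a mixed model could use.

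**The case against.** The strongest case on the other side has five parts.

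*Scope.* A reader might infer that every exit removes the partner. The text does not establish this. Section 13 opens by separating exclusion from withdrawal, and the partner rule is worded for withdrawal. Its place under the exclusion heading makes the wider reading possible, not certain. For a participant who chooses to leave, ending the partner's ratings is also defensible, since section 14 bases data collection on the consent of both. This part stands: the text is ambiguous, and the ambiguity needs fixing.

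*Link to outcome.* A reader might infer that worsening symptoms routinely end participation. Section 13 says only that participants may be excluded when continuing is unsafe, and the worsening rule in section 9 stops the intervention without mentioning exit. Suicidal ideation is not named as an NPI domain; it is only tied to the depression item. So a link is possible, but it is not shown to be usual.

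*Surviving data.* A reader might infer that H2a would have no record of deterioration, or would describe only people who did not deteriorate. That does not follow. Weekly NPI-Q ratings before exit stay on file and belong to the secondary endpoint. Section 17 models NPI measures over time without restricting them to the full NPI, although it does not say that the weekly ratings enter the model.

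*Where the promise sits.* The section 9 sentence stands among MRI risks. Its wording is general, though, and refers to the study and the analysis.

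*Consent terms.* The consent pages are not in the text reviewed, so terms on data after withdrawal may exist there. They would not remove the conflict within the protocol.

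**Conclusion.** The concern holds in a limited form. Sections 9 and 13 conflict, and following section 13 as written gives up ratings on the secondary endpoint that phone follow-up could obtain. For an exit during treatment the loss is every post-baseline full NPI, but not the weekly NPI-Q already recorded.

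Whether this biases H2a or H2b, and by how much, cannot be known from the documents. With about 4 exits, the range runs from 0 for an even split to 0.40 SD if all four fall in one arm and are 2 SD worse. The 0.18 SD worst-tail figure is illustrative, not an expected value. It should not be expressed as a share of the treatment effect, because the plan gives no expected effect on NPI. A mixed model remains valid if exits depend only on recorded ratings. It does not if they follow worsening that was never rated, and no sensitivity analysis is planned for that.

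The primary fMRI endpoints do not depend on the partner, and this is a small mechanistic pilot. The point should be fixed, but it does not undermine the trial.

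**What to change.** 1. Reconcile sections 9 and 13. Replace automatic partner withdrawal with a statement that the partner continues to give the NPI at the scheduled post-intervention and follow-up dates, by phone if preferred, unless the participant or the partner declines. Match the consent wording for both.
2. State whether withdrawal in the partner rule includes exclusion by the investigator. Reconcile the section 9 rule on worsening symptoms with section 13, so that it is clear whether stopping the intervention or a safety exclusion ends all data collection. Clinical decisions stay with the study physician.
3. Record three facts separately: tDCS stopped, MRI not done, all follow-up declined.
4. Include all ratings obtained in H2a, by randomised group. H2b gains less, because it also needs a follow-up scan.

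Cost: protocol and consent wording that needs ethics review, and at most two calls to each of about four partners. Section 12 already budgets the payment, since its $60 maximum covers six ratings at $10, two of them after the intervention. Some partners or participants will refuse, so the gap will shrink but not close. Ratings missed at their scheduled dates cannot be recovered later, so the change is best made while participants are still being followed.

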14. PRIVACY AND CONFIDENTIALITY OF SUBJECTS AND RESEARCH DATA

Data Security: Participant data will be collected with the verbal and/or written consent of the participant. Information pertaining to individual participants will be released with the participant's permission only. All participant data will be identified by a uniquely coded screening ID assigned to each respondent and study ID for participants eligible for enrollment. Access to the master links between name and screening ID as well as between screening ID and study ID will be restricted to the study coordinator, interventionist, and staff involved in screening.

Only trained study personnel will have access to participants' research materials, which will be kept in locked facilities and password protected computer system. Manuals for training staff on different parts of the data collection have already been developed for different studies, which will be assembled for the proposed study.

All participant data (including those collected at the screening) will be collected with the verbal or written consent of the participant and study partner subject. Information pertaining to individual participants will be released with the participant's informed and written consent only. Participant data will be identified by a uniquely assigned study number. Access to the master list of study numbers will be restricted to the PI and study staff and maintained and stored in a lab database (Filemaker, Filemaker Inc.) on Filemaker server at the URMC. The primary source of study data (computer- and questionnaire-based data) will be stored at the lab database (SPSS and Excel). All of these databases are located at a secured site, coordinated through the Medical Center at the University of Rochester. Access to these databases is restricted to the investigators and trained study personnel. Publications or presentations will report only cumulative data or descriptions certain to maintain participants' anonymity. We understand that these data are subject to the Privacy Act, Freedom of Information Act, and other Federal government rules and regulations, and we will comply with those rules and regulations.

None of the information collected in the study will be automatically recorded to EHR since they are all collected in research settings.

For intervention subjects with suspected brain changes identified by CABIN appointed radiologist/neurologist (informed by CABIN technician), we will communicate this information with the subjects, and send them a picture from T1 upon signing the MRI release form. It is the subject's responsibility to share the form with their healthcare providers.

15. DATA AND SAMPLE STORAGE

Blood Specimen: Blood samples will be collected & processed at CRC. Full cryo boxes will then be transferred to 4W-156, -80 freezer in the SON until analysis is completed. **Blood Sample Data:** We will collect information on the following 8 biomarkers: A β 42, t-tau, p-tau, NfL, BDNF, IGF-1, APOE 4, and 2 SCACs [C0 and C5]. In addition, we will measure other blood-based biomarkers such as phospholipids. All data will be stored on an encrypted, password-protected database on the URMC server that is only available to study staff. Individual databases used to house identifying subject information (telephone number, address, date of birth) will also be stored on the URMC server, on a password-protected file management system, accessible only to study staff. Both databases will be managed by the UR information analyst on site. All datasets will be stored pursuant to IRB protocols.

16. DATA AND SAFETY MONITORING PLAN

We propose a Stage 0 pilot intervention study. The study risk is minimal. The safety monitoring of which will be conducted by the research team. All investigators will compose an administrative core to oversee the project, holding regular monthly meeting with the research team. For each monthly meeting, the PI will present an overall progress statement. The issues/concerns related to the safety of participants will include:

- (1) The evidence of safety issues that should be addressed;
- (2) All serious adverse events determine whether individual patients should be removed from the protocol. We acknowledge that there may be rare instances where some emergent situation occurs that was unanticipated regarding the welfare of the participant. In these situations, the UR IRB may be contacted to help resolve the situation.

In addition, the following steps will be taken to protect the confidentiality of data and computer records and participant safety:

- (1) Confidentiality will be assured by the maintenance of the data forms in locked offices, and by restricted access to computerized data. Only core research team members will have access to the name, address, telephone number, and other information corresponding to each identification number. Participants will be fully informed of the study requirements throughout the conduct of the study and will be allowed the opportunity to withdraw from participation if they cannot, or do not comply with the rigors of the research protocol. Handling of data will be limited to the numerical values and statistical summaries.
- (2) Identifiers linking identification codes with individual names will only be available to the PI and study staff who contacts participants.
- (3) The PI has obtained the policies of the UR IRB specifically regarding adverse events associated with the study. The PI will adhere to those policies and maintain a copy of the policies in the studyfile.
- (4) The investigators will protect the health and safety of participants, inform them of information relevant to their continued participation (e.g., newsletters) and pursue the research objective with scientific diligence.
- (5) The following policies required by our IRB and NIH will be adhered to: (1) any adverse events that are serious and unexpected and are related (possibly or probably) to the study will be reported to the IRB and NIH within 15 calendar days; (2) adverse events that are both unexpected and related that are either life threatening or result in death will be reported to IRB and NIH immediately; and (3) for adverse events that do not meet the criteria above will be documented in the summary report submitted to the IRB and NIH annually at the time of the study's continuing review. Because the proposed study is minimal risk, we do not anticipate any serious adverse effects as described in the first two categories from a result of participating in this study.

Expected Adverse Events:

- Temporary tingling or itching sensation from tDCS.
- Dizziness, mild nausea, headache, a metallic taste in their mouth, sensations of flashing lights, heating, and risk of metal projectiles during MRI.
 - Rating criteria for the severity of adverse events:
 - 1 = Mild event, no treatment required;
 - 2 = Moderate event, resolved with treatment;
 - 3 = Severe event, resulted in inability to carry on normal activities, ongoing medical treatment required;
 - 4 = Life threatening or fatal.
 - Attribution of the adverse event to the study:
 - Non-study related = Event clearly not related to doubtfully related to the study;

Study-related = Event possibly, likely, or clearly related to the study.

(6) The PI will ensure that the NIH (funding Institute and Center) is informed of the actions, if any, taken by the IRB as a result of its continuing review, and recommendations that emanate from the monitoring activities.

